## 11. MANAGEMENT AND REPORTING OF ADVERSE EVENTS/ADVERSE REACTIONS FOR TAFAMIDIS-TREATED SUBJECTS

### 11.1. Requirements

The table below summarizes the requirements for recording safety events in the THAOS electronic data record and for reporting safety events on the non-interventional study (NIS) adverse event monitoring (AEM) Report Form to Pfizer Safety. These requirements are delineated for 3 types of events: (1) serious adverse events (SAEs); (2) non-serious AEs (as applicable); and (3) scenarios involving drug exposure, including exposure during pregnancy (EDP), exposure during breast feeding, medication error, overdose, misuse, extravasation, and occupational exposure. These events are defined in the section “[Definitions of Safety Events](#)”

Safety event	Recorded in the THAOS electronic data record	Reported on the NIS AEM Report Form to Pfizer Safety within 24 hours of awareness
SAE	All	All
Non-serious AE	All	None
Scenarios involving exposure to a drug under study, including EDP, exposure during breastfeeding, medication error, overdose, misuse, extravasation; lack of efficacy; and occupational exposure	All (regardless of whether associated with an AE), except occupational exposure	All (regardless of whether associated with an AE)

For each AE, the investigator must pursue and obtain information adequate both to determine the outcome of the AE and to assess whether it meets the criteria for classification as a SAE (see section “[Serious Adverse Events](#)” below).

Safety events listed in the table above must be reported to Pfizer within 24 hours of awareness of the event by the investigator **regardless of whether the event is determined by the investigator to be related to tafamidis**. In particular if the SAE is fatal or life-threatening, notification to Pfizer or its designated representative must be made

immediately, irrespective of the extent of available event information. This timeframe also applies to additional new (follow-up) information on previously forwarded safety event reports. In the rare situation that the investigator does not become immediately aware of the occurrence of a safety event, the investigator must report the event within 24 hours after learning of it and document the time of his/her first awareness of the events.

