### **11.4. Definitions of Safety Events**

#### **11.4.1. Adverse Events**

An AE is any untoward medical occurrence in a patient administered a medicinal product. The event need not necessarily have a causal relationship with the product treatment or usage. Examples of AEs include but are not limited to:

- Abnormal test findings (see below for circumstances in which an abnormal test finding constitutes an AE);
- Clinically significant symptoms and signs;
- Changes in physical examination findings;
- Hypersensitivity;
- Progression/worsening of underlying disease;
- Lack of efficacy;
- Drug abuse;
- Drug dependency.

Additionally, for medicinal products, they may include the signs or symptoms resulting from:

- Drug overdose;
- Drug withdrawal;

- Drug misuse;
- Off-label use;
- Drug interactions;
- Extravasation;
- EDP;
- Exposure during breast feeding;
- Medication error;
- Occupational exposure.

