## 2.2 STUDY OBJECTIVES

The objectives of THAOS are to:

- Describe the population of patients affected with ATTR amyloidoses;
- Enhance the understanding of disease natural history, including the variability and progression of the hereditary and acquired forms of the disease;
- Better understand the genotype – phenotype relationship in ATTRv;
- Compare the progression of disease and overall survival in patients with ATTR amyloidosis with and without liver transplant;
- Foster an international community of medical experts who will develop recommendations on the clinical management of ATTR amyloidoses;
- Provide information to better understand the management and treatment of patients with ATTR amyloidoses through publication of the survey data;
- Provide information on off-label use of tafamidis by identifying patients who do not meet the inclusion criteria for transthyretin amyloid cardiomyopathy (ATTR-CM)
- For tafamidis-treated patients, collect and summarize all AE/SAE data, including for the specific safety concerns outlined in Table 1 Summary of Safety Concerns to be Assessed in THAOS comprising important identified risks, important potential risks, and missing information that includes long-term safety in ATTR-CM patients with **CCI** [REDACTED] Class IV.
- For patients not treated with tafamidis, collect and summarize additional data on the events of interest listed in Table 1.

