**The other subgroups to be considered are as follows:**

- CCI [REDACTED]
- Severe hepatic impairment (only to be used corresponding to tafamidis treated set). The patients with severe hepatic impairment at baseline will be identified by any of the following:
  - The following pre-coded terms on the Gastrointestinal medical history and the Gastrointestinal general assessment forms: Hepatitis, Cirrhosis, Gastrointestinal malignancy, Hepatotoxicity, Other hepatic impairment having severity scale as “severe”.
  - The following terms appearing in the database as entered on the Other Gastrointestinal Medical History or General Assessment forms at baseline and assessed as ‘severe’: “severe impaired hepatic function”, “severe hepatic dysfunction”, “severe liver dysfunction/liver failure”. Other similar terms as identified during the final database lock of this study may be investigated to identify patients with severe hepatic impairment at baseline.
- Patients not on tafamidis at the time of enrollment on THAOS who had a liver transplant prior to enrollment on THAOS
- Patients not on tafamidis at the time of enrollment on THAOS who had a liver transplant after enrollment on THAOS
- Patients not on tafamidis at the time of enrollment on THAOS without any liver transplant either before or after enrollment on THAOS
- Patients treated with tafamidis at any time in THAOS and with a liver transplant prior to first dose of tafamidis
- Patients treated with tafamidis at any time in THAOS and with a liver transplant after the first dose of tafamidis
- Patients treated with tafamidis at any time in THAOS and never had a liver transplant
- Off-label use of 80/61 milligram (mg) of tafamidis (only to be used corresponding to tafamidis treated set) defined as:
  - Patients not classified as predominantly cardiac or mixed phenotype at the first date of dosing with a dose of 80/61 milligram (mg) of tafamidis.
- Predominantly neurologic at baseline who become mixed phenotype post baseline\*
- Predominantly cardiac at baseline who become mixed phenotype post baseline\*

Sample size in a subgroup needs to be at least 10 in order to have sufficient data to provide descriptive statistics, listings will be provided for smaller subgroups.

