### **Exposure**

Duration of exposure (in years) among patients receiving tafamidis while enrolled in THAOS will be summarized (excluding time when the patient was part of clinical trial or Compassionate Use/Early Access Program) by starting dose using the tafamidis treated set by phenotype at enrollment and overall, CCI [REDACTED] and either predominantly cardiac or mixed phenotype at enrollment, tafamidis treated set for patients who had severe hepatic impairment at baseline, tafamidis treated set by liver transplantation status (liver transplant prior to first dose of tafamidis/liver transplant after the first dose of tafamidis/no liver transplant).

Additionally the duration of treatment with 20 mg and 61 mg/80 mg will be summarized separately for patients with off label use.

The duration of exposure (in years) will be calculated as:

Sum of all non-missing days when tafamidis was taken (excluding days of other clinical trial/compassionate use participation) / 365.25

Summary of exposure-adjusted Incidence rates (per patient-year) AEs and SAE for Treatment Emergent Adverse events (All causalities) and mortality for tafamidis treated set will be provided.

A separate listing will be provided for duration of exposure listing for patients who switched from 61/80 mg to 20 mg.

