### Adverse Events & Serious Adverse Events

All adverse events will be coded according to the latest Medical Dictionary for Regulatory Activities (MedDRA) version at the time of analysis.

Adverse events (all causality and treatment-related) will be summarized by severity and starting dose using the tafamidis treated set by phenotype at enrollment and overall, CCI [REDACTED] and either predominantly cardiac or mixed phenotype at enrollment, tafamidis treated set for patients who had severe hepatic impairment at baseline, tafamidis treated set by liver transplantation status (liver transplant prior to first dose of tafamidis/liver transplant after the first dose of tafamidis/no liver transplant).

Separate summaries will be provided for all AEs, treatment related AEs, all SAEs, treatment related SAEs, AEs leading to dose reduction, AEs leading to withdrawal of tafamidis (temporarily or permanently, or delayed) and AEs leading to tafamidis dose interruptions.

Listings will be provided for adverse events corresponding to all enrolled patients and for patients with off-label usage of tafamidis. A separate listing of SAEs will also be provided for tafamidis treated set.

The following AE summary tables will be provided corresponding to some of the important potential risks using the tafamidis treated set.

- For **hepatotoxicity** using the search criteria: MedDRA SMQ (Standardized MedDRA Query) [Broad and narrow] Drug related hepatic disorders – comprehensive search. The derivations and conventions related to the search criteria will follow the programming specifications done in the Periodic Safety Update Report (PSUR) 12 for tafamidis.
- For **reproductive and developmental toxicity and lactation**:
  - MedDRA SMQ (Broad and narrow): Congenital, familial and genetic disorders; Foetal disorders; Neonatal disorders, Neonatal exposures via breast milk.
  - MedDRA Preferred terms (PTs): Exposure during pregnancy, Exposure via father, Foetal exposure during delivery, Foetal exposure during pregnancy, Foetal exposure timing unspecified, Maternal exposure before pregnancy, Maternal exposure during delivery, Maternal exposure during pregnancy, Maternal exposure timing unspecified, Drug exposure before

- pregnancy, Exposure via breastmilk, Maternal drug affecting foetus, Maternal exposure during breastfeeding
- The derivations and conventions related to the search criteria will follow the programming specifications done in the PSUR 12 for tafamidis.

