  - For **changes in thyroid function**, using the search criteria: MedDRA SMQ (Broad and narrow): Thyroid dysfunction. The derivations and conventions related to the search criteria will follow the programming specifications done in the PSUR 12 for tafamidis.
  - For **off-label use**, MedDRA PTs: product use in unapproved indication, Product use issue, Intentional product use issue, Drug effective for unapproved indication, Drug ineffective for unapproved indication

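### The off-label-use adverse event table in SAP 8.2.6 is built on five preferred terms, none worded 'off-label use', so an event coded to such a term would be left out of it

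*SAP*

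**What the plan says.** SAP 8.2.6, under Adverse Events & Serious Adverse Events, lists four AE searches to be run on the tafamidis treated set. The last is for off-label use, and its whole definition is: "MedDRA PTs: product use in unapproved indication, Product use issue, Intentional product use issue, Drug effective for unapproved indication, Drug ineffective for unapproved indication". AEs are to be coded in the MedDRA version current at the time of analysis.

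Off-label use also appears elsewhere in the SAP:

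- Section 2.2 sets the objective: "Provide information on off-label use of tafamidis by identifying patients who do not meet the inclusion criteria" for ATTR-CM.
- Section 5.4 defines the off-label subgroup: "Patients not classified as predominantly cardiac or mixed phenotype at the first date of dosing with a dose of 80/61 milligram (mg) of tafamidis".
- Section 8.2.6, Exposure: "Additionally the duration of treatment with 20 mg and 61 mg/80 mg will be summarized separately for patients with off label use".
- Section 8.2.6, Adverse Events: "Listings will be provided for adverse events corresponding to all enrolled patients and for patients with off-label usage of tafamidis".

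The protocol uses the words once, in 11.4.1, as a bullet under this lead-in: "Additionally, for medicinal products, they may include the signs or symptoms resulting from". The table in Protocol 11.1 names the situations that are recorded and reported whether or not an AE occurred: "Scenarios involving exposure to a drug under study, including EDP, exposure during breastfeeding, medication error, overdose, misuse, extravasation; lack of efficacy; and occupational exposure". Off-label use is not among those named.

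**The concern.** A table titled off-label use should collect the events whose coded term says off-label use. This one is tied to five other terms. A programmer following the SAP literally would select those five and nothing else, so an event coded to an off-label-use term would be absent from the table that a reader would consult for it.

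At stake is whether one descriptive safety table in the final report of a post-authorisation safety study is complete. The report will also carry a second off-label count, from the 5.4 subgroup. The SAP does not say how the two relate, so a reader who finds that they differ has no explanation.

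**Working it through.** The plan states no figure to reproduce, and no sample size or error rate is involved. The check is a reading of the term list against the other places that bear on it.

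**1. Sort the five terms (SAP 8.2.6).**

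| Type | Terms | Count |
|---|---|---|
| Names an unapproved indication | product use in it; drug effective for it; drug ineffective for it | 3 |
| General product-use issue | product use issue; intentional product use issue | 2 |
| Worded as off-label use | none | 0 |

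3 + 2 + 0 = 5, so 0 of 5 terms carry the words in the table's title. The three specific terms concern indication only. Off-label use of another kind, for instance by dose or population, would enter only if it were coded to one of the two general terms.

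**2. Is there another route into the table?** The hepatic and thyroid searches each use a standardised MedDRA query. The reproductive-toxicity search uses such queries together with a term list. All three refer to the conventions of the twelfth periodic safety update report. The off-label search has no query and no such reference. The SAP can leave a search open when it wants to: the severe hepatic impairment definition in 5.4 allows similar terms found at database lock to be considered. The off-label list has no such allowance and is therefore closed.

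**3. Would sites produce the missing term?** Protocol 11.4.1 treats off-label use as a possible origin of signs or symptoms. A site following it would record the sign or symptom, which codes to its own term. Protocol 11.1 does not name off-label use as a reporting scenario. Such entries are possible, but nothing makes them the expected entry.

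**4. What would be lost?** Let A be the treated-set AE reports coded to the five terms and B those coded to an off-label-use term. The table shows A, whereas its title implies A + B. The shortfall is B. The documents give neither A nor B, nor how site wording is coded, so B may be zero and its size cannot be computed. Events in B remain in the all-AE summaries for the treated set and in the AE listing for all enrolled patients.

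**5. Does the 5.4 subgroup fill the gap?** Partly. It does not depend on MedDRA coding and it answers the 2.2 objective. But it is confined to the 80/61 mg dose and to phenotype at the first such dose, so any off-label use outside that rule is not counted there.

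**The case against.** The strongest case against the point is that little depends on this table. The SAP 2.2 objective is to be met by identifying patients, and the 5.4 subgroup does that from dose and phenotype. That subgroup has its own baseline definition (8.2), exposure summary and AE listing. No event disappears from the report. Three of the five terms already describe use outside an approved indication, which is close to what the objective targets. Whether MedDRA has a separate term for off-label use, and how site text would code, is not stated in the documents. The contrast with the other searches is also imperfect, because the reproductive-toxicity search relies partly on an explicit term list. All of this stands, and it limits the size of the point.

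Three stronger readings are tempting, and the documents do not support them:

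- **That the protocol tells sites to report the words off-label use.** Protocol 11.4.1 gives it only as a possible source of signs or symptoms, and 11.1 does not name it.
- **That the table is shown to undercount.** No document gives the number of affected reports, and an assumed share would only return the assumption.
- **That a difference between the table and the 5.4 subgroup would be a contradiction.** One counts coded AE reports and the other counts patients by dose and phenotype. They can differ even with a complete term list.

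What the objection does not remove is that the list is closed, carries no stated reason, and omits the wording of its own title. The 5.4 subgroup is not a full substitute, because it covers only 80/61 mg.

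**Conclusion.** The point holds as a minor gap in one supplementary descriptive table. By the SAP's own rule, any AE coded to an off-label-use term falls outside the off-label-use table while remaining in the all-AE outputs. The number of reports affected is unknown and may be none. The main off-label objective is not compromised, since it is served mainly by the 5.4 subgroup.

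The conclusion assumes that the five terms will be applied as written, with no further terms from unpublished programming specifications. An actual loss would also require that the MedDRA version used has a term to which off-label use codes, distinct from the five listed, and that some report was coded to it. The correction is worth making because it costs almost nothing and has no effect if no event codes to the added term.

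**What to change.** In SAP 8.2.6, add to the off-label-use list the preferred term to which off-label use codes in the MedDRA version used at analysis.

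Add a footnote to the table stating that it counts coded AE reports in the treated set, that the 5.4 subgroup counts patients by dose and phenotype at 80/61 mg, and that the two counts therefore need not agree.

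The cost is one term in a search list and one footnote. No data collection, analysis set or other table changes.

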### Deaths

Summaries on the number (%) of patients who died, by primary cause, and whether deaths were ATTR related will be provided using all enrolled patients, tafamidis treated set by phenotype at enrollment and overall, tafamidis untreated set by phenotype at enrollment and overall, CCI [REDACTED] and either predominantly cardiac or mixed phenotype at enrollment, tafamidis treated set for patients who had severe hepatic impairment at baseline, tafamidis treated set by liver transplantation status (liver transplant prior to first dose of tafamidis/liver transplant after the first dose of tafamidis/no liver transplant), tafamidis untreated set by their liver transplantation status (liver transplant prior to enrollment/liver transplant after enrollment/no liver transplant).

A separate listing of deaths will also be provided for the tafamidis treated set.

### Hematology and Chemistry

Change from baseline by yearly intervals of the hematology and biochemistry laboratory parameters will be provided using the tafamidis treated set by starting dose.

### Blood Pressure

Change from baseline by yearly intervals of the systolic and diastolic blood pressure will be provided using tafamidis treated set by starting dose and tafamidis untreated set.

### Electrocardiogram

For ECG, the following summaries will be provided at baseline and by yearly intervals:

- Any abnormalities in rhythm (Y/N)
- Sinus pause (Y/N)
- Atrial flutter (Y/N)

- Atrial fibrillation (Y/N)
- Atrial premature beat (Y/N)
- Junctional rhythm (Y/N)
- Ventricular tachycardia (Y/N)
- Ventricular premature complexes (Y/N)
- Other rhythm abnormality (Y/N)
- Pacemaker with normal function (Y/N)
- Low voltage (Y/N)
- Conduction abnormalities(Y/N)
- Types of conduction abnormalities
- Morphology abnormalities
- Types of morphology abnormalities
- Pathologic Q-Waves observed
- Types of P-Q wave abnormalities
- ST Segment T Wave abnormalities
- Types of ST Segment abnormalities

Also for the following parameters corresponding to ECG, summary statistics for the baseline and change from baseline by yearly intervals will be provided:

- QRS Axis
- PR
- QRS
- QT
- QTc

The summaries will be done using the tafamidis untreated set with predominantly cardiac or mixed phenotype at enrollment, tafamidis treated set with predominantly cardiac or mixed phenotype at enrollment, CCI [REDACTED] and either predominantly cardiac or mixed phenotype at enrollment, tafamidis treated set for patients who switched from predominantly neurologic to mixed phenotype and tafamidis untreated set for patients who switched from predominantly neurologic to mixed phenotype.

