### ATTR-PN

The hereditary forms of ATTR amyloidosis are autosomal dominantly inherited diseases with a variable penetrance that can affect multiple generations in a family and have a substantial impact on patients and their families. Val30Met (substitution of methionine for valine at position 30) is the most common mutation associated with ATTR-PN, with symptom onset usually in the third to fourth decade of life, depending on the mutation carried and the patient's ethnic background.

The main feature of ATTR-PN is progressive sensorimotor and autonomic neuropathy. Sensory neuropathy typically starts in the lower extremities followed by motor neuropathy within a few years. Autonomic neuropathy quite often accompanies the sensory and motor deficits. ATTR-PN is more frequently observed in certain areas of Portugal, Sweden, and Japan but has been identified throughout the world. Although penetrance varies greatly among geographic and ethnic foci, the outcome of the disease is invariably progressive and fatal. The lifespan for patients is severely shortened, with death occurring within a mean of 10-15 years from the first symptoms.

Disease-modifying therapies for ATTR-PN include TTR stabilizer tafamidis, orthotopic liver transplantation, RNA interference (RNAi)-based drugs, and transthyretin-directed antisense oligonucleotide drugs. Tafamidis meglumine was approved in the European Union (EU) on 16 November 2011 for the treatment of ATTR in adult patients with Stage 1 symptomatic polyneuropathy to delay peripheral neurologic impairment. Currently, it is approved for ATTR-PN in over 40 countries worldwide. Subsequently, Tegsedi (inotersen) and Onpattro (patisiran) for the treatment of hereditary ATTR amyloidosis in patients with polyneuropathy (ATTR-PN) have also been approved in the EU and US.

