## **ATTR-CM**

ATTR-CM occurs when the amyloid fibrils infiltrate the myocardium, leading to diastolic dysfunction progressing to, heart failure, restrictive cardiomyopathy, and death. ATTR-CM, also known as familial amyloid cardiomyopathy (FAC), is a late-onset disease with symptoms typically occurring in patients over 60 years old. This disease can be inherited as an autosomal dominant trait caused by mutation in the TTR gene (commonly the Val122Ile mutation which occurs with high frequency [prevalence of 3.9%] in African-Americans); however, a mutation in TTR gene is not a pre-requisite for developing ATTR-CM. In the elderly, wild-type (normal) TTR may become structurally unstable resulting in deposition of amyloid fibrils primarily in heart tissue and leading to restrictive cardiomyopathy and heart failure.

Wild-type ATTR amyloidosis (previously known as senile systemic amyloidosis (SSA) or senile cardiac amyloidosis, is diagnosed based on positive bone scintigraphy (Perugini grade  $\geq 2$ ) or confirmed ATTR amyloid by tissue biopsy and immunohistochemical staining, and characteristic echocardiographic abnormalities in the absence of a TTR gene mutation and a plasma cell dyscrasia. The clinical presentation of

wild-type ATTR amyloidosis is similar to variant ATTR-CM, with the disease primarily affecting elderly males.

Combined heart and liver transplantation is a treatment option for ATTR-CM, however is limited by organ availability and significant patient co-morbidity.

Tafamidis is currently the only approved treatment for ATTR-CM with approvals in a growing number of countries worldwide including but not limited to: Japan (March 2019) for tafamidis meglumine 80 mg daily in patients with wild-type and variant forms of ATTR-CM; the US (May 2019) for tafamidis meglumine 80 mg daily and tafamidis 61mg daily for the treatment of the cardiomyopathy of wild-type or hereditary transthyretin-mediated amyloidosis in adults to reduce cardiovascular mortality and cardiovascular-related hospitalization; and the EU (February 2020) as a line extension to tafamidis 61 mg daily for the treatment of wild-type or hereditary transthyretin amyloidosis in adult patients with cardiomyopathy.

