### **7.3. Role of THAOS in the Tafamidis European Union Post-Marketing Commitment**

On 21 July 2011 the European Union (EU) Committee for Medicinal Products for Human Use (CHMP) adopted a positive opinion, recommending the granting of a marketing authorization for the medicinal product tafamidis 20 mg capsule intended for the treatment of ATTR amyloidosis in adult patients with Stage 1 symptomatic polyneuropathy to delay peripheral neurologic impairment. Granting of marketing authorization for tafamidis was made under exceptional circumstances. The collection of safety data in THAOS will fulfill part of the post-marketing commitment to the CHMP for tafamidis. This non-interventional (NI) study is designated as a Post-Authorisation Safety Study (PASS) and is a commitment to the EMA. Additionally, data in ATTR-CM patients collected via this registry will further characterize important potential risks and missing information with tafamidis (see Section 8) as agreed with the EMA during the line extension procedure for ATTR-CM.

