## **8 STATISTICAL METHODOLOGY AND STATISTICAL ANALYSES**

### **8.1 STATISTICAL METHODS**

The key objectives of the survey are to better understand the natural history of ATTR (hereditary and wild-type forms) and the progression of disease in this patient population. Analysis of clinical outcomes will be conducted on all enrolled patients with available data. Outcomes will be examined separately for the untreated and tafamidis treated sets, as well as for appropriate subgroups within these set. Outcomes will include results of the key clinical, functional and QoL assessments used to define progression of disease.

Data will be summarized descriptively.

Continuous variables will be summarized using descriptive statistics ie, number of non-missing values and number of missing values [ie, n (missing)], mean, median, standard deviation (SD), minimum, maximum and 10th and 90th percentile.

Qualitative variables will be summarized by frequency counts and percentages. Unless otherwise specified, the calculation of proportions will be based on non-missing values.

In case the analysis refers only to certain visits, percentages will be based on the number of patients still present in the study at that visit, unless otherwise specified. Sample size in a subgroup needs to be at least 10 in order to have sufficient data to provide descriptive statistics, listings will be provided for smaller subgroups.

Kaplan-Meier estimates (product-limit estimates) will be presented including the median time with two-sided 95% confidence intervals (CIs), if the number of events are at least 5.

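### Yearly ECG abnormality percentages in the treated cardiac/mixed set pool starting doses with very different maximum follow-up, so they can drift with who is left; the size and direction cannot be known from the documents

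*SAP*

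**What the plan says.** SAP 8.2.6, Electrocardiogram, introduces the categorical findings (rhythm abnormality, atrial fibrillation, low voltage, conduction and morphology abnormalities, pathologic Q waves and others) with: "For ECG, the following summaries will be provided at baseline and by yearly intervals". Only QRS axis, PR, QRS, QT and QTc also get change from baseline. Treated patients enter as the "tafamidis treated set with predominantly cardiac or mixed phenotype at enrollment", with no division by starting dose. As far as the extracted table can be read, the ECG row of SAP 8.2.8 has no mark under treated by starting dose either.

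Other safety outputs are divided. Laboratory values "will be provided using the tafamidis treated set by starting dose", and blood pressure "will be provided using tafamidis treated set by starting dose and tafamidis untreated set".

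SAP 8.1 adds that, for analyses at particular visits, "percentages will be based on the number of patients still present in the study at that visit". The same section bases proportions on non-missing values unless otherwise specified. Under either rule the denominator changes from year to year.

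The dates come from the Protocol. In 7.1: "Tafamidis meglumine was approved in the European Union (EU) on 16 November 2011". Section 7.3 identifies that product as the "tafamidis 20 mg capsule intended for the treatment of ATTR amyloidosis in adult patients with Stage 1 symptomatic polyneuropathy". For the higher dose, 7.1 lists "Japan (March 2019) for tafamidis meglumine 80 mg daily in patients with wild-type and variant forms of ATTR-CM", then the US in May 2019 and the EU in February 2020. Data collection ends on 16 June 2023 (section 6).

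**The concern.** A row of percentages labelled baseline, Year 1, Year 2 and so on invites reading along the row. That is safe only if the same kind of patient stands behind each column. Here the two starting-dose groups have very different maximum follow-up, so the 61/80 mg starters leave the table within a few years whatever happens to their ECGs.

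The groups may well differ. The lower dose was authorised for polyneuropathy and the higher for cardiomyopathy. Protocol 7.1 describes onset of Val30Met polyneuropathy usually in the third to fourth decade, and cardiomyopathy typically after age 60. An apparent fall or rise in atrial fibrillation or conduction disease over years on tafamidis could then be partly or wholly a change of patient mix, and the visible outputs would not let a reader tell. THAOS is a designated post-authorisation safety study, so such a row may be read as safety information.

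**Working it through.** The plan states no figure on this point, so there is nothing to reproduce. The check has two steps.

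**Step 1: how far each group can reach.** In Appendix 2, Year k covers study days above 365.25 × (k − 0.5) up to 365.25 × (k + 0.5). The longest possible study day is 16 June 2023 minus the start date, plus 1.

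| Earliest start | Days | Years | Last window |
|---|---|---|---|
| 16 Nov 2011 (EU, 20 mg) | 4,231 | 11.58 | Year 12 |
| 1 to 31 Mar 2019 (Japan, 80 mg) | 1,569 to 1,539 | 4.30 to 4.21 | Year 4 |
| 1 to 31 May 2019 (US, 80/61 mg) | 1,508 to 1,478 | 4.13 to 4.05 | Year 4 |
| 1 to 29 Feb 2020 (EU, 61 mg) | 1,232 to 1,204 | 3.37 to 3.30 | Year 3 |

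The extra 28 days after last dose in the note closing 8.2.6 change none of these windows. Reaching Year 5 requires a start by about 16 December 2018.

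**Step 2: what pooling can do.** Assumptions, none of them in the documents: starts spread evenly from approval to 16 June 2023, no drop-out or death, and every patient's ECG finding constant. With L the length of the start period (11.58 years for 20 mg; 4.29 years for 61/80 mg, from 1 March 2019), the fraction able to reach Year k is (L − (k − 0.5)) / L, or 0 if negative.

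- 61/80 mg starters, Years 1 to 5: 88.4%, 65.1%, 41.8%, 18.5%, 0%. For Year 4: (4.293 − 3.5) / 4.293 = 0.185.
- 20 mg starters, Years 1 to 5: 95.7%, 87.0%, 78.4%, 69.8%, 61.1%, falling to 0.7% at Year 12.

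The pooled percentage at Year k is the sum of (share × fraction reaching k × prevalence) over the two groups, divided by the sum of (share × fraction reaching k). With equal shares and assumed prevalences of 50% (20 mg) and 80% (61/80 mg), Year 4 gives (0.698 × 50 + 0.185 × 80) / (0.698 + 0.185) = 56.3%.

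| 61/80 mg share | Prevalence 20 mg / 61/80 mg | Year 0 | 1 | 2 | 3 | 4 | 5 onward | Drift (points) |
|---|---|---|---|---|---|---|---|---|
| 25% | 50% / 80% | 57.5 | 57.1 | 56.0 | 54.5 | 52.4 | 50.0 | −7.5 |
| 50% | 50% / 80% | 65.0 | 64.4 | 62.8 | 60.4 | 56.3 | 50.0 | −15.0 |
| 75% | 50% / 80% | 72.5 | 72.0 | 70.7 | 68.5 | 63.3 | 50.0 | −22.5 |
| 50% | 60% / 70% | 65.0 | 64.8 | 64.3 | 63.5 | 62.1 | 60.0 | −5.0 |
| 75% | 80% / 50% | 57.5 | 58.0 | 59.3 | 61.5 | 66.7 | 80.0 | +22.5 |
| any | 60% / 60% | 60.0 | 60.0 | 60.0 | 60.0 | 60.0 | 60.0 | 0 |

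Under the same assumptions, dividing by starting dose makes each group flat: in the second row, 50% throughout for 20 mg, and 80% at Years 0 to 4 then no data for 61/80 mg. Losses within a dose group remain, and only a matched comparison deals with those.

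**The case against.** A reader might infer that the ECG trend does change for this reason, that it is fixed by approval dates, or that Year 5 onward holds only patients taking 20 mg. The documents support none of these.

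- **Drift is conditional.** It needs a prevalence difference by starting dose. Everyone in the set is cardiac or mixed at enrollment, and for variant disease SAP 5.4 makes rhythm disturbance, heart failure or dyspnea part of that classification. The 20 mg starters here are therefore already selected for cardiac involvement, and the gap may be small. This stands.
- **The Year 4 limit applies to starters on commercial 61/80 mg.** Patients who switch up from 20 mg keep their earlier Day 1 and can contribute later. A first dose in a trial might also set an earlier Day 1, although trial data are excluded (SAP 2.1). The Protocol's approval list is expressly not exhaustive. This stands.
- **Part of the ECG output is already within-patient.** PR, QRS, QT, QTc and QRS axis get change from baseline, which covers part of conduction. It does not cover atrial fibrillation, low voltage or Q waves.
- **The SAP is descriptive and tests nothing** (section 4). True, and it limits the seriousness; a descriptive row can still mislead.
- **Redaction.** One ECG subgroup is blacked out, so the absence of a dose split or matched baseline can be asserted only for visible text.
- **The blood-pressure precedent is imperfect.** The text divides by starting dose; the extracted summary row shows no such mark. Laboratory values are the cleaner precedent.

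**Conclusion.** The point holds in conditional form. On the documents' own dates and windows, commercial 61/80 mg starters can fill at most Years 0 to 4, while 20 mg-era starters can run to Year 12. The yes/no ECG findings are pooled across the two with a changing denominator. The percentages can therefore drift through composition alone if prevalence differs by starting dose. In the scenarios tried, the shift from Year 0 to Year 5 runs from 0 to 22.5 points, in either direction. Those sizes rest on assumed prevalences (50% to 80%), an assumed 61/80 mg share (25% to 75%), even starts and no drop-out; they show what is possible and do not predict the result. This is a worthwhile, inexpensive improvement to a descriptive table and does not invalidate an analysis.

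**What to change.** In SAP 8.2.6, Electrocardiogram, and the matching row of 8.2.8:

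1. Keep the planned yearly percentages for the full treated cardiac/mixed set.
2. Present them also by starting dose, as for laboratory values.
3. For each year, among patients with both a baseline and that year's ECG, add the baseline percentage of those same patients and the shift (absent to present, present to absent), with n shown.

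No new data are needed. The cost is SAP wording, reshaped tables and more columns. Some late-year dose cells will fall below 10, where SAP 8.1 replaces statistics with listings. The matched rows also lose patients. SAP 8.2 takes treated baseline from within 3 weeks either side of starting tafamidis, ECGs are optional, and visits are roughly annual, so the loss may be large and selective. The matched rows should therefore sit beside the full-set percentages and not replace them.
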